7.3.3 FOLLOW-UP STUDY VISITS

Study visit number at 3, 4, 5 occurring at months 3, 6, and 9 after enrollment:

At the follow-up visits, the following activities will occur/be performed:

- Study specific history of HZO treatment.
- Study specific anterior segment ophthalmic exam.
- Assessment of post herpetic neuralgia score and review of medications taken for PHN.
- Returned study medication pills will be counted to assess medication compliance. Diaries will be returned.
- Assessment for possible medical events of interest
- Assessment for possible primary endpoints.
- Assessment for possible SAEs.
- Study participants will be dispensed an adequate supply of study medication and will receive instructions to take 2 pills once daily. in addition to any other medication(s). At the discretion of the investigator, dosage may be adjusted to one pill twice daily or once daily and appropriate study participant instruction sheet will be provided (see MOP).
- Study participants will receive a diary to record when study medication is taken.
- If the study participant had a baseline eGFR of 45-59 repeat eGFRs will be completed prior to the 3, 6, 9 month study visits.
 - o If eGFR is 45 or above, study medication will be continued.
 - If eGFR is less than 45, the study medication will be discontinued, and the eGFR will be repeated within one week. If on repeat testing the eGFR:
 - is 45 or more, the study medication will be resumed, and eGFR will be repeated within 30 days of the next study visit.
 - is less than 45, study participant will be given a prescription to visit their local study designated laboratory for monthly eGFR testing until it is 45 or more. In addition, study participants will be told to see their primary care doctor for management of their kidney disease. The study medication will not be resumed, and the study participant will continue to be followed in the study.
- An appointment to return during a specified window of days for their three-month follow-up visit will be scheduled.
- The study participant will be instructed to continue their non-study treatment.

The importance of compliance with the study medication and visits, will be emphasized at each study visit. Study participant's contact information will also be confirmed at each study visit (see MOP).

Visit 6 (12 month follow-up visit):

At this visit, study medication will be discontinued. The visit will be the same as the 3, 6, and 9- month follow-up visits, with the addition of:

• Study specific ophthalmic exam including direct fundus exam. If visual acuity is 2 or more lines lower than enrollment visual acuity, then a routine refraction will be done in the study eye. If visual acuity is not improved by a routine refraction, then a dilated fundus will be performed.

- In study participants with enrollment eGFR 45-59, an eGFR test will be done prior to this visit:
- if 45 or above, will not be repeated (this is not part of routine care).
- If less than 45, eGFR will be repeated within one week. If on repeat testing the eGFR:
 - is 45 or more, it will not be repeated.
 - is less than 45, study participants will be given a prescription to visit their local study designated laboratory for monthly eGFR testing until it is 45 or more. In addition study participants will be told to see their primary care doctor for management of their kidney disease, and the study participant will continue to be followed.
- The study participant will be instructed to continue their non-study treatment.

Visit 7 (15 month follow-up visit):

The visit will be the same as the 3, 6, and 9- month follow-up visits (please note there is no study medication involved and eGFR testing is not repeated (see MOP).

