Oral antiviral medications are generally very safe and can be used in patients with impaired renal function, but their dosage needs to be adjusted. For valacyclovir, a suppressive regimen of 1000 mg daily is reduced to 500 mg daily, in study participants with creatinine clearance < 30. Study participants on dialysis or with a baseline eGFR < 45 within one month prior to enrollment will be excluded from the study. On the basis of recommendations of a geriatrician, infectious disease specialist, and nephrologist, study participants with eGFRs 45 -59 will be eligible, based on assessment of potential risk/benefit ratio. Elderly patients are at increased risk for and most negatively impacted by HZO and often have reduced eGFR. Approximately 25% of people age 70 years and older can be estimated to have eGFRs between 45 and 59 (51). Study participants with a baseline eGFR of 45-59 will have repeat eGFRs prior to the three, six, nine, 12-month study visits. If the eGFR decreases to less than 45, the eGFR will be repeated. If on repeat testing the eGFR is less than 45 the study medication will be discontinued. Study participants will be told to see their primary care doctor and have eGFR repeated monthly until it is 45 or more. The study participant will continue to be followed, but the study medication will not be restarted.

The package insert contains a warning that acute renal failure can occur in the elderly, with or without reduced renal function. Nephrotoxicity is more frequent after intravenous than oral acyclovir. Serum creatinine >1.5 of the upper limit of normal occurred in 0.2% of HZ patients on 1000 mg oral valacyclovir tid and 0% of genital HSV patients on oral valacyclovir suppression with 1000 mg daily. Dehydration contributes to nephrotoxicity.

Study participants will be provided with a participant instruction sheet, which will include directions to maintain adequate hydration to decrease the likelihood of nephrotoxicity.

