The investigational plan is specifically designed to manage and minimize risks through careful selection of study participants and suppressive antiviral treatment regimen, thorough training of study investigators and coordinators, adherence to the pre-determined time points to assess study participant clinical status, and regular clinical monitoring by study Coordinating Center (CC) personnel and the Data and Safety Monitoring Committee (DSMC). Suppressive treatment with valacyclovir 1000 mg daily of immunocompetent individuals age 18 years and older is FDA approved and recommended for herpes simplex virus (HSV) genital disease. This study evaluates the efficacy and safety of valacyclovir, at the same dose used for HSV suppression, for study participants with a different diagnosis, HZO, for which valacyclovir is approved at a higher dose, for a short duration. HZO patients are generally older than HSV patients, with approximately mean age of onset of HZO of 52 years compared to ocular HSV with a mean age onset of 37 years (2, 4, 53).

In order to minimize risks of valacyclovir in an older population of study participants, a baseline eGFR will be obtained prior to enrollment. If the eGFR is 60 or more, i.e. normal, it will not be repeated for study purposes. In order not to unfairly exclude many elderly study participants by requiring an eGFR of 60 or more, a baseline eGFR of 45 or more is an eligibility criterion. Study participants with eGFRs between 45-59 will have repeat eGFR testing every 3 months during treatment with the study drug. If the eGFR decreases to less than 45, the eGFR will be repeated. If repeat eGFR is 45 or more, the study medication will be continued, and the eGFR will be repeated prior to the next study visit. If on repeat testing the eGFR is less than 45 the study medication will be discontinued. Study participants will be told to see their primary care doctor and have eGFR test repeated monthly until it is 45 or more. The study medication will not be restarted, and the participant will continue to be followed for safety assessments.

There are no known study-related risks in addition to the use of the study medication, oral valacyclovir and blood testing.

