6.1.8 DOSE ADJUSTMENTS/MODIFICATIONS/DELAYS

Study investigators will be trained and study participants will be instructed regarding dose adjustments of study medication.

Use of Divided Dose of Study Medication for Intolerance

If the study participant has mild to moderate side effects to the study medication, the medication may be temporarily discontinued. The study participant may take one pill twice daily, instead of two pills once daily, as it may be better tolerated.

Use of Reduced Dose of Study Medication for Intolerance

If the study participant has mild to moderate side effects to the study medicine when taken in divided doses, the medication may be temporarily discontinued. The study participant may take a reduced dose of one capsule daily.

Discontinuation of Study Medication due to Intolerance

If intolerance to the study medication is moderate or worse after restarting the study medication in divided doses and reducing the dose, the study medication will be permanently discontinued. The study participant will be treated at the discretion of ophthalmologists involved in their care, and continue to be followed. Open label use of other antivirals after study medication is discontinued will be collected and monitored.

Discontinuation of Study Medication

If the study participant develops a contraindication to valacyclovir during the course of the study (See 5.2.). The study medication will be permanently discontinued and the study participant will continue to be followed.

Discontinuation due to Pregnancy

If a study participant becomes pregnant, the study medication will be discontinued and the study participant will continue to be followed. If a study participant thinks she may be pregnant, a pregnancy test will be performed.

Discontinuation due to Worsening Chronic Kidney Disease

If a study participant develops worsening chronic kidney disease with confirmed eGFR less than 45, the study medication will be discontinued and the study participant will continue to be followed.

Discontinuation due to Acute Kidney Failure

If a study participant develops acute kidney failure, and requires temporary or permanent dialysis, the study medication will be discontinued and the study participant will continue to be followed.

Temporary Discontinuation due to Vaccination Against Zoster

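### Sections 7.3.3 and 2.3.1 give opposite instructions on study drug between a first follow-up eGFR below 45 and the repeat result; the eGFR entry window also differs between sections

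*Combined protocol and SAP*

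**What the plan says.** The rule concerns participants enrolled with a baseline eGFR of 45-59. Under 2.3.1 (Valacyclovir and Renal Insufficiency) they "will have repeat eGFRs prior to the three, six, nine, 12-month study visits". Section 7.3.1 places each test within 30 days of the visit.

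Four places then say what follows a low value:

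- **7.3.3, visits at months 3, 6 and 9:** "If eGFR is less than 45, the study medication will be discontinued, and the eGFR will be repeated within one week". If the repeat "is 45 or more, the study medication will be resumed". If the repeat is again low, drug is not restarted.
- **2.3.1, Protections Against Risk:** a first low value leads to a repeat test. Then "If repeat eGFR is 45 or more, the study medication will be continued"; otherwise "If on repeat testing the eGFR is less than 45 the study medication will be discontinued".
- **2.3.1, Valacyclovir and Renal Insufficiency:** the same order (repeat, then stop on the second low value), with nothing on drug status while the repeat is awaited.
- **6.1.8:** "If a study participant develops worsening chronic kidney disease with confirmed eGFR less than 45, the study medication will be discontinued". Nothing is said about an unconfirmed value.

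For Visit 6 (month 12), 7.3.3 says "The visit will be the same as the 3, 6, and 9- month follow-up visits, with the addition of" a list of items. That list states that "an eGFR test will be done prior to this visit" and gives a one-week limit for repeating a low value. It includes no step stopping drug while the repeat is awaited.

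On entry, 2.3.1 excludes an eGFR below 45 within one month before enrollment. Exclusion criterion 3b in 5.2 uses 3 months. Sections 7.2.1, 7.3.1 and Table 1 footnote 4 work with a test no more than 30 days old.

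**The concern.** A coordinator holding one eGFR result below 45 finds two different instructions in the same protocol. One takes the participant off drug pending the repeat and the other leaves the participant on it. This subgroup was admitted with reduced renal function on a stated risk/benefit judgment (2.3.1), and 8.5 names acute kidney failure as the predominant safety concern.

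Three consequences follow for the trial record:

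- Section 14.3 counts any noncompliance with the protocol as a deviation, so a site that follows one section departs from the other.
- Section 8.1.1 requires reporting of adverse events that lead to a temporary stop. Whether a stop occurs at all would depend on the section the site read.
- Section 10.4.2 plans analyses of the impact of drug discontinuation by arm, and 6.1.10 measures adherence by pill count. Both would then partly reflect site practice.

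The entry-window mismatch raises a separate and smaller question: whether a low value more than a month old excludes a candidate.

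**Working it through.** No formula applies. The check sets the current texts side by side.

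| Place | First value below 45 | Deadline for repeat | Repeat 45 or more | Repeat below 45 |
|---|---|---|---|---|
| 7.3.3, months 3, 6, 9 | drug stopped | one week | drug restarted | not restarted |
| 2.3.1, Protections Against Risk | repeat only | none | drug kept going | stopped, not restarted |
| 2.3.1, Renal Insufficiency | repeat only | none | not stated | stopped, not restarted |
| 6.1.8 | not addressed | none | not addressed | stopped (confirmed value) |
| 7.3.3, Visit 6 list | repeat; drug status not stated | one week | no further test | referral and monthly tests |

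**Step 1: is there a true conflict?** Yes, between the first two rows. Restarting presupposes an interruption and continuing presupposes none. The two texts give opposite drug status over the same interval.

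**Step 2: how far does it reach?** Only from the first low value to the repeat result. In the last column, every section that addresses on-treatment drug status after a second low value stops it. The other 2.3.1 paragraph and 6.1.8 do not directly contradict 7.3.3, since they are silent on the interval. Both do tie stopping to the second or confirmed value.

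**Step 3: how many scheduled tests?** Months 3, 6, 9 and 12 give 4 tests. The stop is explicit at months 3, 6 and 9, which is 3. The remainder is 4 − 3 = 1, month 12. That sample may be drawn up to 30 days before Visit 6 (7.3.1), and drug ends at the visit, so a low result can arrive while drug is still being taken. The statement that Visit 6 matches the earlier visits suggests that the stop carries over. The separate Visit 6 eGFR steps, which omit it, suggest that it may not.

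**Step 4: can the interval be bounded?** No. The one-week limit in 7.3.3 governs the repeat test, not the return of its result or the restart of drug, and 2.3.1 has no limit. The documents give no count of expected participants or of low values.

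**Step 5: entry window.** One month and 30 days are practically the same, so the discrepancy is with the 3 months in criterion 3b. The windows are nested and a site can satisfy them together. What 3b means is unclear. Take as an illustration a candidate with an eGFR of 42 two months ago and 47 last week:

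- If 3b is a look-back, it excludes this candidate, while 7.3.1 read alone makes the candidate eligible.
- If 3b limits the age of the test, it is simply looser than the 30-day limit.

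**The case against.** The strongest case is that the direct conflict is one pair of texts. Section 2.3.1 is introductory risk narrative, while 7.3.3 is the visit procedure that sites work from and the only one of the two with a repeat deadline. The Manual of Operations and Procedures may settle the matter. Section 6.1.8 can be read as describing final discontinuation, which all sections share. Month 12 could be read as inheriting the earlier steps. A candidate who meets 3b is excluded whatever 7.3.1 says, because meeting any exclusion criterion is enough.

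Much of this limits the scope, and those limits are accepted. The conflict covers only the wait for the repeat. Section 6.1.8 is silent on that interval, month 12 is unclear and not contradictory, and the entry-window point is minor.

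It does not remove the main point. The text in 2.3.1 is written as a directive under a heading about protecting participants, and no section gives 7.3.3 precedence. Section 6.1.8 lists temporary stops for intolerance, vaccination and open-label antivirals but none for a first low eGFR, so it does not settle the question. The manual is not among the documents, so actual confusion at sites is unproven. Whatever it says, the protocol text still contradicts itself.

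**Conclusion.** The contradiction is real and should be fixed. For participants with a baseline eGFR of 45-59, 7.3.3 and 2.3.1 give opposite drug instructions between a first value below 45 and the repeat result. It applies explicitly at 3 of the 4 scheduled tests, with the fourth unclear. Neither the length of the interval nor the number of participants affected can be derived from the documents. The all-randomized primary analysis and the sample size are unaffected. The consequences are for participant safety handling, deviation and discontinuation records, and exposure.

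The conclusion rests on the protocol text alone, assuming that no rule of precedence exists elsewhere. It takes no view on which clinical rule is right. The entry-window mismatch is an accurate secondary point on which the main finding does not depend.

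**What to change.** - Bring both paragraphs of 2.3.1, section 6.1.8 and section 7.3.3 to one stated action on a first eGFR below 45 and one deadline for the repeat test.
- State whether the interim stop applies to the test drawn before Visit 6.
- Give one entry window across 2.3.1, exclusion criterion 3b, 7.2.1, 7.3.1 and Table 1 footnote 4, and say whether 3b is a look-back or a limit on the age of the test.
- Check that the Manual of Operations and Procedures carries the same wording.

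The sponsor decides which clinical rule applies. The cost is wording changes in 2.3.1 (two places), 5.2, 6.1.8 and 7.3.3, a clarifying line in 7.2.1, 7.3.1 and the table footnote, and a memo to sites. The analysis and the sample size do not change.

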7.3.4 FINAL STUDY VISIT

Visit 8 (18 month final study visit)

The visit is the same as the 15 month follow-up visit (Visit 7). This visit is the last study visit for the participant and the study completion form will be filled out (see MOP).

7.3.5 EARLY TERMINATION VISIT

This visit is similar to the 18-month visit (See MOP).

7.3.6 NON-STUDY VISIT (UNSCHEDULED/SCHEDULED VISIT)

At non-study visits, a standard office medical exam will be completed (routine care) (See MOP). A CRF for non-study visit will be completed by the study staff. Additional CRFs may be required if a primary endpoint may have occurred at the time of the non-study visit.

7.3.7 SCHEDULE OF EVENTS TABLE

Source documents include medical records, images and all other information necessary to reconstruct and evaluate the clinical trial. Study monitors will compare data entered in electronic CRF's to information in source documents to verify the accuracy of trial data.

Please see Table 1 for Schedule of Events.

Table 1: Schedule of Events.

Procedures	Screening/consent (Visit 1)	Enrollment/Randomization (Visit 2)	3-month Follow-up (Visit 3)	6-month Follow-up (Visit 4)	9-month Follow-up (Visit 5)	12-month Follow-up (Visit 6)	15-month Follow-up (Visit 7)	18-month Follow-up (Visit 8)
Informed consent	X							
Study specific review of medical records ¹	Х	х						
Study specific review of demographics	Х							
Review of inclusion/exclusion criteria ²	Х	х						
Order pregnancy test ³	Х							
Order serum creatinine blood test for eGFR determination ⁴	X ^{4,5}							
Repeat eGFR prior to visit only if baseline eGFR = 45-59 ⁵			х	х	х	х		
Study specific history of HZO treatment		х	Х	х	х	х	х	Х
Study specific ophthalmic exam		X^6	X ⁷	X ⁷	X ⁷	X ⁸	X ⁷	X ⁷
PHN score and review of medication history for PHN		Х	Х	Х	Х	Х	Х	Х
Randomization		х						
Medication dispensed and instruction sheet provided		х	х	х	х			
Assessment of possible medical events			х	х	х	х	х	Х
Assessment of possible primary endpoints			х	х	х	Х	х	Х
Assessment of possible SAEs			Х	Х	Х	Х	Х	Х

¹ Study specific review of the participant's medical history is reviewed at the screening visit and the case report form is completed at the enrollment visit. If the study participant is ineligible, the form is not completed.

² Inclusion/exclusion criteria are reviewed at the screening visit and the case report form is completed during the enrollment visit. If the study participant is ineligible at the screening visit, the form is completed then.

³ A serum pregnancy test is required of women of child-bearing potential, who have provided written informed consent and are found to be eligible. The pregnancy test should preferably be done 2-3 days after a menstrual cycle. A urine dipstick test for pregnancy will be conducted by study staff if a study participant suspects pregnancy at the time of a study visit.

⁴ A serum creatinine blood test for eGFR determination will not be required if one has been completed in the past 30 days and the results are available for review.

⁵ Study participants with an eGFR of 45-59 will be enrolled in the study, but asked to have repeat testing at intervals throughout the study.

⁶ At enrollment/randomization, the study specific ophthalmic exam of the study eye consists of routine manifest refraction, anterior segment ophthalmic exam, dilated fundus exam and pachymetry.

⁷ At visits 3, 4, 5, 7 and 8, the study specific ophthalmic exam consists of an anterior segment ophthalmic exam.

⁸ At visit 6, the study specific ophthalmic exam of the study eye consists of a direct fundus exam. If visual acuity is 2 or more lines lower than enrollment visual acuity, then a routine refraction will be done in the study eye. If visual acuity is not improved by a refraction, then a dilated fundus will be performed.

7.4 JUSTIFICATION FOR SENSITIVE PROCEDURES

Not applicable.

7.5 CONCOMITANT MEDICATIONS, TREATMENTS, AND PROCEDURES

The FDA-approved label for the use of valacyclovir does not list contra-indications to the use of other medications concomitantly with valacyclovir.

While it is recommended that study participants with HZO receive acute high dose antiviral treatment within 72 hours of the onset of the rash for seven days, and study participants will be asked their history regarding this, it will not be required for entry into the study, as it would make many participants ineligible. Optimal medical treatment aside from acute antiviral treatment has not been determined for HZO. The study medication will be given to study participants in addition to standard treatment. It is the purpose of this study to evaluate the efficacy of prolonged suppressive antiviral treatment, to determine whether it should become optimal medical therapy in the future. Aside from the antiviral medications valacyclovir, acyclovir, and famciclovir, all other concomitant systemic medications are allowed during the study. Study participants who require topical steroids will be strongly recommended to be treated with prednisolone acetate 1% or loteprednol 0.5% at the discretion of their study investigator. Study participants who develop dendriform epithelial keratitis will be recommended to be treated with topical ganciclovir (0.15%) five times daily until healed and then two times daily for two weeks. These topical steroids and antiviral medications are standard care.

